8.12.1.2 Number of days until conjugated bilirubin > 2 mg/dL

Time (in days) to when conjugated bilirubin levels > 2 mg/dL is the time from the randomization date to the date of first occurrence of conjugated bilirubin levels > 2 mg/dL (confirmed by a second sample collected 7 days after the first sample). Death during hospitalization will be considered a competing risk. Patients alive will be censored if bilirubin levels > 2 mg/dL are not observed during the study using the last follow-up date as the censoring time.

The cumulative incidence function until conjugated bilirubin > 2 mg/dL will be estimated using the Aalen estimator (Aalen, 1978). The cause-specific hazard will be estimated using the subdistribution hazard model according to Fine and Gray with factors treatment, underlying disease group (No NEC / NEC) and the interaction term (Fine & Gray, 1999).

The number of patients with conjugated bilirubin levels > 2 mg/dL, the number of patients who died, the number of patients censored, the median time to event determined from the cumulative incidence function and the hazard ratio and its 95% confidence interval estimated determined from the Fine and Gray-model will be presented in a summary table.

8.12.2 Other Secondary Safety Variables

For each patient, the ratio of the number of independent bloodstream infections and the number of days on study medication will be computed. The ratio, as well as the number and incidence of patients with at least one bloodstream infection will be summarized descriptively by underlying disease group, treatment arm and study phase. A data listing of number of bloodstream infections and number of days on study medication will be included.

The number and incidence of patients who complete PN treatment without lipid minimization, as well as the cumulative number of days of PN administration without lipid minimization will be summarized descriptively statistics by underlying disease, treatment arm and study phase. A corresponding data listing will be included.

The number of patients who need to be withdrawn from the study due to elevated conjugated bilirubin levels will be summarized with descriptive statistics by underlying disease, treatment arm and study phase.

Statistical Analysis Plan

FK Study Identifier: SMOF-018-CP3

8.12.3 Area under the curve of conjugated bilirubin for time period in which levels are > 1.5 mg/dL

The area under the curve (AUC_{>1.5}) is defined as the area between conjugated bilirubin concentrations > 1.5 mg/dL and the horizontal line at 1.5 mg/dL, restricted by the time point of study withdrawal, if applicable. The AUC_{>1.5} will be calculated using the Riemann method¹⁰, which is the same as the trapezoidal rule. An AUC value will only be used if there was no more than one conjugated bilirubin value missing. Descriptive summary statistics by treatment group and study phase and a detailed data listing will be presented.

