- **Early discontinuation:**

Should conjugated bilirubin exceed 2 mg/dL (> 2 mg/dL), a confirmatory analysis must be performed after 7 days. The patient's dose will remain at 1 g/kg/day until analysis of the confirmatory blood sample. If the confirmatory analysis reveals that conjugated bilirubin increased further by at least 1 mg/dL, then the patient has to be removed from the study immediately and may be treated with an alternative lipid emulsion at the investigator's discretion. If not, the patient continues to receive study medication.

- **Weaning of lipids and PN:**

As soon as the patient receives 80 mL/kg/day oral/enteral feeding and achieved tolerance (i.e. at least 3 days) the dose of study drug must be reduced to 1 g/kg/d.

As soon as patient receives 100 mL/kg/day oral/enteral feeding and achieved tolerance (i.e. at least 3 days) study drug must be stopped completely.

Duration of Treatment:

The expected administration of lipid emulsions for each study patient should be 28 days. If PN is still indicated after 28 days, patients may receive the study drug for up to 84 days.

Patients:

Hospitalized neonates and infants, expected to require PN for 28 days

Clinical Study Protocol SMOF-018-CP3

Smoflipid 20% lipid injectable emulsion

Inclusion Criteria:

1. Neonates and infants, expected to require PN for 28 days
2. Postmenstrual age \geq 24 weeks
3. Birth weight \geq 750g
4. Gastrochisis, duodenal, jejunal or ileal atresia, volvulus, spontaneous intestinal perforation or necrotizing enterocolitis (Bell's stage 2B or higher)
5. At least 80% of nutritional needs at Baseline are met with PN
6. Signed and dated informed consent obtained from at least one parent or legal guardian

Exclusion Criteria:

1. Conjugated bilirubin > 0.6 mg/dL
2. Any known pre-, intra- or posthepatic complication that will increase conjugated bilirubin levels > 0.6 mg/dL during study participation
3. Suspected liver disease or liver damage based on either AST, ALT, or GGT exceeding 2.5x upper limit of normal range
4. Active bloodstream infection demonstrated by positive blood culture at screening
5. Cystic fibrosis
6. Meconium ileus
7. Serum TGs > 250 mg/dL
8. Cyanotic congenital heart defect
9. Severe renal failure as evidenced by creatinine > 2.0 mg/dL
10. History of shock requiring vasopressors
11. Anasarca
12. Extracorporeal Membrane Oxygenation (ECMO)
13. Known inborn errors of metabolism
14. Known congenital viral infection

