10.4 Withdrawal of Patients from the Study

Patients withdrawn from study after randomization but before receiving any study drug will be counted as “early drop-outs”. These patients will be replaced and will not undergo additional assessments.

The patient’s parent or guardian may voluntarily withdraw the patient from participation in the study or prevent the administration of study medication at any time without needing to provide any reason.

If the Investigator has to withdraw a patient from the study, or if the patient’s parent(s) or legal guardian(s) refuses to have the patient continue with study participation, patient’s parents or legal representatives should be asked to allow that the assessments for the Final Visit the day after receiving the last dose of study medication are completed. The reason(s) for study withdrawal must be documented.

Patients who are withdrawn from the study due to AEs or SAEs will be treated and followed according to established medical practice to evaluate the course of the AE and ensure reversibility or stabilization (also see Section 13).

The following are justifiable reasons for the Investigator to withdraw a patient from the study:

- Intolerable AEs/SAEs
- Deteriorating liver function (see below)
- Unacceptable risk/benefit ratio
- Major protocol deviation(s)

Major protocol deviations are those that may significantly impact the completeness, accuracy, and/or reliability of the study data or may affect the patient’s rights, safety, or well-being. In case of any potential major deviation, the Investigator has to notify the CRA immediately.

Fresenius Kabi reserves the right to discontinue the entire study for internal reasons at any time (see also Section 16.3).

Withdrawal Due to Deteriorating Liver Function

If conjugated bilirubin levels exceed 2 mg/dL, a confirmatory sample must be assessed after 7 days. If conjugated bilirubin levels have increased by at least 1 mg/dL, the Investigator must withdraw the patient from the study so the patient can receive an alternative lipid emulsion according to standard of care. If conjugated bilirubin levels increased less than 1 mg/dL, the patient will remain in the study and continue to receive study medication. Weekly conjugated bilirubin analyses must be performed until the patient’s conjugated bilirubin level is again \leq 1.5 mg/dL.

Clinical Study Protocol SMOF-018-CP3
Smoflipid 20% lipid injectable emulsion

11 Study Drugs and Medication

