12.3.2 Laboratory Variables

12.3.2.1 Standard Laboratory Values Including Conjugated Bilirubin

Determination of the standard laboratory values will be assessed using established validated techniques at the local laboratory of the site except for **plasma conjugated bilirubin** which **will be assessed using established validated techniques at the central laboratory**:

The following parameters will be assessed at the local laboratory:

Biochemistry: total bilirubin, AST, ALT, GGT, ALP, TGs, creatinine, glucose, CRP

Clinical Study Protocol SMOF-018-CP3 **Smoflipid 20% lipid injectable emulsion**

Hematology: CBC (total white blood cells, total red blood cells, hemoglobin, hematocrit, mean corpuscular volume, mean corpuscular hemoglobin, mean corpuscular hemoglobin concentration, red blood cell distribution width and platelets)

Coagulation: INR

The valid normal ranges and a certification from the local laboratory will be obtained before start of the study.

The blood samples needed for the assessment of conjugated bilirubin at the central laboratory will be obtained at the same time as the blood sample for the local laboratory, to reduce the number of needle pricks. 1ml of full blood will be required for the analysis.

An exact description of the methodology for drawing, handling and shipping of the samples as well as the methodology used for the analysis of conjugated bilirubin at the central lab is outlined in the lab manual.

The investigators must review all laboratory results. Laboratory values outside the normal ranges must be assessed concerning their clinical significance by the respective investigator and the assessment must be documented on the lab report / in the patient's medical file. If the out of range value is considered clinically significant then it is an AE (see Section 13) and must be documented in the eCRF (see Section 12.4.1).

Assessments are preferably done at each visit. If the blood draw is from the PN/lipid infusion line, then lipid (study drug) should be held for 4 hours prior to the time of blood sampling. Study investigators must draw additional blood samples to monitor TG levels during initial increase in lipid dose and if TG increases beyond 250 mg/dL. The Investigators must also draw blood samples for blood cultures if a patient shows clinical symptoms of a bloodstream infection.

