8.6 Treatment Exposure and Compliance

The duration of exposure (days) to a study drug, total amount of study drug administered and average daily dosage of study drug (per kg body weight) administrated will be summarized with descriptive statistics by underlying disease and treatment arm. For patients with conjugated bilirubin levels > 2 mg/dL, the cumulative dose administrated before the primary endpoint is reached (bilirubin >2 mg/dL) will be summarized by underlying disease and treatment arm.

Duration of exposure will be calculated as the difference between the date of last infusion of a study drug and the date of first infusion with a study drug plus 1 day. A data listing for treatment exposure will be included.

The duration, dose, and type of pre-treatment will be extracted from prior and concomitant medication form and summarized with descriptive statistics by underlying disease and treatment group. The frequency and percentage of patients who received PN for pre-treatment will be summarized by treatment group.

Compliance will be assessed by

- the ratio of the actual number of study drug infusions over the expected number of study drug infusions expressed as percent
- the ratio of the actual cumulative dose over the expected cumulative dose

evaluated separately over the initial and extension phase, resp., and summarized descriptively by treatment group and study phase.

Infusion of study drug will be expected on a given Study Day over the treatment period (Day 1 to Day 28 for initial treatment phase and Day 29 to Day 85 for treatment extension phase). Treatment with a study drug on a given Study Day will be considered an actual study drug infusion, provided any interruption of study drug infusion does not exceed 4 hours. Any interruption of the infusion of study drug longer than 4 hours will be documented and explained in the eCRF.

Compliance data will be provided in a data listing by patient.

Dose interruption (dose delay and modification) will be summarized with descriptive statistics (frequency and percentage) by treatment group.

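### The conjugated bilirubin AUC above 1.5 mg/dL stops at an undated withdrawal that rising bilirubin itself triggers, so infants withdrawn early are either cut short or left out, depending on an unclear missing-value rule

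*SAP*

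**What the plan says.** SAP 8.12.3 takes the area between conjugated bilirubin and the 1.5 mg/dL line by the trapezoidal rule, "restricted by the time point of study withdrawal, if applicable". It then adds: "An AUC value will only be used if there was no more than one conjugated bilirubin value missing". Results are descriptive, by arm and phase, with a listing.

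The variable lists in Protocol 6.2.2 and SAP 5.2.2 refer only to time spent above 1.5 mg/dL, with no cut at withdrawal. SAP 7.4 says who is a dropout but not when the dropout occurs. SAP 8.12.1.2, by contrast, does name the censoring time for its time-to-event variable.

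On withdrawal, Protocol 10.4 says: "If conjugated bilirubin levels have increased by at least 1 mg/dL, the Investigator must withdraw the patient from the study". Protocol 1 (Early discontinuation) and 11.3 set the same trigger, which follows a first value above 2 mg/dL. Protocol 7.1, 9, 12.2.7 and 13.3.5 provide for bilirubin follow-up of infants who are still raised when treatment ends.

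SAP 8.12.2 also plans a separate count, split by disease stratum, arm and phase: "The number of patients who need to be withdrawn from the study due to elevated conjugated bilirubin levels will be summarized with descriptive statistics".

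**The concern.** A cumulative area grows with observation time. Here a rapid rise in the same analyte ends that time, so the cut is informative. An infant who triggers withdrawal early in a phase may contribute a smaller area than a milder infant who stays, or may contribute none.

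Two gaps in the text make this worse. The cut has no date, so two programmers could compute different areas from the same data. The missing-value rule does not say whether samples that would have fallen after withdrawal are missing, so the same infant may be included or excluded. If the arms differ in bilirubin-driven withdrawals, their mean AUCs are then hard to compare.

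**Working it through.** The documents give no AUC figure, so there is nothing to reproduce. The bilirubin paths below are assumptions and show only how the definition behaves.

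**1. Candidate cut dates**
- The confirmatory-sample day.
- The day the result is known. Protocol 12.3.2.1 sends the assay away ("The blood samples needed for the assessment of conjugated bilirubin at the central laboratory will be obtained at the same time" as the local sample), and the turnaround is not given.
- The next-day visit, at which Protocol 10.4 asks that "the assessments for the Final Visit the day after receiving the last dose of study medication are completed".
- The Follow-Up Visit, 7 days after End of Treatment (Protocol 12.2.7).

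**2. Formula.** Interpolate linearly between samples and sum the area above 1.5, with the crossing point interpolated. Units are mg/dL x days. The trigger path is the smallest qualifying rise, 2.1 to 3.1.

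**3. First value above 2 on Day 8, confirmed Day 15.** The Day 1 value is set at 0.6, the eligibility ceiling in Protocol 10.3.
- Days 1 to 8: the line crosses 1.5 after 7 x 0.9/1.5 = 4.2 days, leaving 2.8 days. Area = 0.5 x 0.6 x 2.8 = 0.84.
- Days 8 to 15: (0.6 + 1.6)/2 x 7 = 7.70.
- Cut at Day 15: **8.54**.
- To Day 29: + 0.5 x 1.6 x 14 = **19.74** if the level falls linearly to 1.5, or + 1.6 x 14 = **30.94** if it stays at 3.1. The cut loses 11.2/19.74 = 57% to 22.4/30.94 = 72%.
- Milder infant flat at 2.1 who stays: 0.84 + 0.6 x 21 = **13.44**.
- Cut date, level held at 3.1 (1.6 per day): Day 16 gives 10.14, Day 18 gives 13.34, and a Follow-Up Visit on Day 23 gives 8.54 + 8 x 1.6 = 21.34. That is 2.5 times the Day 15 value. The reversal against 13.44 disappears after (13.44 - 8.54)/1.6 = 3.06 days.

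**4. First value above 2 on Day 15, confirmed Day 22.** The Day 8 value is set at 1.0.
- Days 8 to 15: the line crosses after 7 x 0.5/1.1 = 3.18 days, leaving 3.82 days. Area = 0.5 x 0.6 x 3.82 = 1.15.
- Days 15 to 22: 7.70. Cut at Day 22: **8.85**.
- To Day 29: + 5.6 = **14.45**, or + 11.2 = **20.05**. The loss is 39% to 56%.
- Milder infant flat at 2.1: 1.15 + 0.6 x 14 = 9.55. The reversal disappears after 0.44 days, before a next-day cut.

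**5. Missing-value rule,** counting scheduled samples within a phase and assuming no other gaps:

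| Withdrawn | Later samples in phase | If these count as missing | If they do not |
|---|---|---|---|
| Day 15 | 22, 29 | no AUC | kept, cut (8.54) |
| Day 22 | 29 | kept, cut (8.85) | kept, cut (8.85) |
| Day 29 | none in initial phase | no loss | no loss |
| Extension, Day 36 | 43, 57, 71, 85 | no AUC | kept, cut |
| Extension, Day 71 or 78 | 85 | kept, cut | kept, cut |

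**6. Counter-examples with the timing of step 4.** Stayers flat at 1.6 or 1.8 score 1.46 and 4.59, below the cut 8.85. An infant rising from 5.0 to 5.9 does not meet the trigger, stays, and scores 69.17 to Day 29.

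**The case against.** **Stopping at withdrawal is defensible.** A withdrawn infant may receive another lipid emulsion, and the AUC belongs to an as-treated safety set. This stands. The truncated AUC is a legitimate in-study summary if it is declared as one and dated.

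**The plan already shows withdrawals.** Counts by arm and phase, time to a confirmed value above 2 mg/dL, bilirubin summaries and an AUC listing are all planned, with no p-values. This stands and limits the impact, but a separate count does not correct a mean AUC.

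**Later values are less secure than they look.** The weekly-sampling text in Protocol 12.2.5 concerns infants weaned from study drug. Section 13.3.5 requires follow-up but gives no frequency. Section 12.2.7 comes closest to weekly sampling, but its wording is circular. Section 10.4 only has parents asked to allow the final assessments. This stands: some values may be unavailable.

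**Other documents may settle the rule.** SAP 7.10.3 leaves missing values to the blinded data review, whose minutes are not available here.

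A reader might go further on three points that the documents do not support:
- *That the AUC ranks the sickest infants lowest.* The trigger is a rise and not a level, and step 6 shows orderings that are correct.
- *That every early withdrawal is understated.* If later visits count as missing, the Day 15 and Day 36 infants are excluded instead.
- *That SAP 8.6 fixes the AUC phases.* Its bounds, "Day 1 to Day 28 for initial treatment phase and Day 29 to Day 85 for treatment extension phase", define expected infusion days for compliance.

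**Conclusion.** The point holds in a limited form. The cut is undated and depends on the outcome, and early bilirubin-driven withdrawals are either understated or left out, according to how the missing-value rule is read. On the assumed minimum-rise paths the loss to Day 29 is 57% to 72% for withdrawal on Day 15 (if that infant is kept) and 39% to 56% on Day 22, with the cut at the confirmatory sample. It is nil in the initial phase for Day 29.

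These figures rest on the assumed paths, linear interpolation, and a later course between a linear fall to 1.5 by Day 29 and a flat 3.1. Neither the size nor the direction of any difference between arms can be computed, because no withdrawal counts are given. This is a descriptive secondary safety variable, so the remedy is a worthwhile low-cost improvement and not a correction on which the trial's main conclusions depend.

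**What to change.** 1. Keep the withdrawal-truncated AUC, declare it an in-study summary, name the date used for the cut, and state the day bounds of each phase for this variable.
2. State that samples no longer due after withdrawal do not count as missing.
3. Add one supplementary AUC above 1.5 mg/dL from Day 1 to Day 29 for the safety set, and from Day 29 to Day 85 for infants who entered the extension phase. Take the Screening value as the starting value, since the schedule has no Day 1 conjugated bilirubin sample. Use the follow-up values under Protocol 7.1, 9, 12.2.7 and 13.3.5. Score zero for infants never above 1.5 mg/dL and after a documented return to 1.5 or lower. List deaths and losses before the horizon separately.
4. Read both AUCs beside the withdrawal counts already planned by arm and phase.

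The cost is SAP wording and one extra programmed summary, with no new samples requested. There are three downsides. Some values after withdrawal are obtained on another lipid emulsion, so the supplementary AUC describes the assigned strategy and not study drug alone. Some later values may be unavailable. Zero after a return to 1.5 or lower assumes no rebound.

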8.12.4 Adverse Events, Serious Adverse Events, Deaths

All reported terms (investigator descriptions) for AEs will be coded using the version of the Medical Dictionary for Regulatory Activities (MedDRA) at database closure and will be summarized descriptively.

A treatment-emergent adverse event (TEAE) is an event that emerges during treatment, having been absent pre-treatment, or worsens relative to the pre-treatment state.

For all AE summaries, events will be counted only once for a given patient by primary system organ class and preferred term. When an AE occurs more than once for a patient, the maximum severity and causality will be used. Missing severity will not be imputed but counted as a separate category. AEs which are not rated as “not related” will be reported as related according to the study protocol and sponsor standards.

The following summaries will be presented with numbers and percentage of patients with the event and number of reported events for each system organ classification and preferred term by underlying disease group and treatment group:

- All AEs
- All TEAEs
- TEAEs leading to discontinuation from the study
- TEAEs by relation to study procedure
- TEAEs by relation to study drug (relationship was reported as “related” or “unrelated”).
- TEAEs by CTCAE severity
- TEAEs by relation to study drug and CTCAE severity
- TEAEs occurring with an incidence > 5 % within any treatment arm
- All serious TEAEs (see Section 13.1.2 of the protocol)
- Serious TEAEs by relation to study drug

Statistical Analysis Plan

FK Study Identifier: SMOF-018-CP3

- TEAEs with fatal outcome

In addition, the number and percentage of patients with the event of the following TEAEs of special interest (syndromes reported as AEs) will be presented by treatment group:

- all major neonatal morbidities
- bronchopulmonary dysplasia
- retinopathy of prematurity
- intraventricular hemorrhage
- periventricular leukomalacia
- necrotizing enterocolitis
- late-onset sepsis in premature and low birth weight neonates.

The following AEs will also be presented by treatment group for each subgroup of ethnicity and race category, respectively:

- All AEs
- All TEAEs
- TEAEs leading to discontinuation from the study
- TEAEs by relation to study procedure
- TEAEs by relation to study drug
- TEAEs by CTCAE severity
- All serious TEAEs (see Section 13.1.2 of the protocol)
- TEAEs with fatal outcome
- TEAEs of special interest, as defined above

All AEs will be presented in data listings by patient. Separate data listings will be created for deaths, serious adverse events (SAEs, death excluded), AEs leading to discontinuation from the study, and AEs of special interest. The Listings of AEs of special interest will also include birth weight.

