6.2.2 Secondary Variable(s)

Secondary variables include:

Efficacy:

- Body weight (change from Baseline)
- Body length (change from Baseline)
- Head circumference (change from Baseline)
- Time to full enteral or oral feeds
- Fatty acids in plasma and red blood cell membranes (change from Baseline)
- Holman index

Safety:

- Length of stay in hospital
- Ratio of number of independent bloodstream infections / number of days on study medication
- Ratio of the number of patients with 1 or more bloodstream infections / number of patients on study medication
- Number of patients who complete PN treatment without lipid minimization
- Number of patients who need to be withdrawn from the study due to elevated conjugated bilirubin levels
- Area under the curve of conjugated bilirubin for time period in which levels are > 1.5 mg/dL
- Cumulative number of days patients are administered a lipid dose without lipid minimization
- Time to conjugated bilirubin > 2 mg/dL (confirmed by a second sample collected 7 days after the first)
- Conjugated bilirubin
- Total bilirubin
- Serum TGs
- Aspartate aminotransferase (AST)
- Alanine aminotransferase (ALT)
- Gamma-glutamyl transferase (GGT)
- Alkaline phosphatase (ALP)
- Blood glucose
- Blood urea nitrogen (BUN)
- Creatinine
- C-reactive protein (CRP)
- Sterols including phytosterols
- α -tocopherol
- Collection of AE data
- Incidence of bronchopulmonary dysplasia (BPD)
- Incidence of retinopathy of prematurity (ROP)
- Incidence of intraventricular hemorrhage (IVH)

Clinical Study Protocol SMOF-018-CP3 **Smoflipid 20% lipid injectable emulsion**

- Incidence of periventricular leukomalacia (PVL)
- Incidence of necrotizing enterocolitis (NEC)
- Incidence of late-onset sepsis in premature and low birth weight neonates

7 Study Design

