7.1 Description of the Study Design

This is a prospective, randomized, controlled, double-blind, parallel-group, phase 3 multicenter study to compare safety and efficacy of Smoflipid to Intralipid in hospitalized preterm and term neonates/infants requiring 28 days of parenteral nutrition.

Treatment group 1: Smoflipid (investigational drug)

Treatment group 2: Intralipid (control drug)

The study drugs, Smoflipid and Intralipid, are lipid emulsions for infusion and will be provided in 100-mL bags. Detailed information on dose of study drug, packaging, and labelling is provided in Section 11.

The study population will be hospitalized preterm and term neonates/infants who are expected to require PN for at least 28 days. Randomization will be stratified depending on the underlying disease to ensure that those diseases are evenly distributed in both treatment groups.

Randomization group 1: No necrotizing enterocolitis (NEC)

Randomization group 2: NEC

Criteria for stratification into randomization group 2:

At least one of the following clinical signs present:

- Biliious gastric aspirate or emesis
- Abdominal distension
- Occult or gross blood in stool (no fissure)

And

At least one of the following radiographic findings present:

- Pneumatosis intestinalis
- Hepato-biliary gas
- Pneumoperitoneum

Patients who do not meet criteria for randomization group 2 will be stratified to randomization group 1.

Clinical Study Protocol SMOF-018-CP3 **Smoflipid 20% lipid injectable emulsion**

At the Screening Visit, the signed and dated patient informed consent will be collected from the parent or guardian, demographics including race and ethnicity, medical history, prior medication, physical examination, vital signs, body weight, body length, and head circumference will be measured and documented and a blood sample will be collected to assess the eligibility of the patient (refer to Section 10.3).

Within 72 hours of the Screening Visit, the Day 1 Visit must take place, during which the eligibility of the patient must be confirmed, taking into consideration the result of the blood sample analysis. Upon confirmation of eligibility, an additional blood sample will be collected for determination of sterol, and α -tocopherol and fatty acids before the patient's random allocation to a treatment group and first infusion of study drug. Patients will receive PN, including study drug, and have their body weight assessed.

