10.2 Inclusion Criteria

1. Neonates and infants, expected to require PN for 28 days
2. Postmenstrual age ≥ 24 weeks
3. Birth weight ≥ 750 g

Clinical Study Protocol SMOF-018-CP3
Smoflipid 20% lipid injectable emulsion

4. Gastroschisis, duodenal, jejunal or ileal atresia, volvulus, spontaneous intestinal perforation, or NEC (Bell's stage 2B or higher)
5. At least 80% of nutritional needs at Baseline are met with PN
6. Signed and dated informed consent obtained from at least 1 parent or legal guardian

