6.2 Safety Analysis Set

The safety analysis set will consist of all randomized patients who received at least one dose of study medication. Patients will be assigned as actually treated. The analysis of secondary safety endpoints will be performed using the safety analysis set.

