7 STATISTICAL CONSIDERATIONS AND DEFINITIONS

All data will be evaluated descriptively and in an exploratory way. Point estimates of differences between treatment groups and corresponding two-sided 95%-confidence intervals will be presented for the primary and key secondary efficacy endpoints. Statistical hypotheses will not be tested and p-values will not be reported.

The analysis of the primary and secondary efficacy endpoints will be performed using both the ITT analysis set and the per protocol set. The analysis of the secondary safety endpoints will be performed using the safety set.

Descriptive statistics will be displayed to provide an overview of the efficacy and safety results by treatment group, stratum and overall. For categorical parameters, these will consist of the number and percentage of patients in each category. The denominator for percentages will be based on the number of patients in the corresponding analysis set, missing will be displayed as a category. For continuous parameters, descriptive statistics will include number of patients with number of non-missing values, mean, standard deviation, median, minimum, and maximum.

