8.12 Analysis of Secondary Safety Variables

The analysis of the secondary safety endpoints will be performed using the safety analysis set. All analysis of the secondary safety endpoints will be descriptive, no statistical hypothesis testing will be performed. Unless otherwise stated, safety endpoints will be presented using data from the initial and extension phase combined. For all safety endpoints data from both stages of the group-sequential design will be combined.

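### The late-onset sepsis row is named for preterm and low-birth-weight infants, but its percentage is taken over the whole safety set

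*SAP*

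**What the plan says.** Protocol 6.2.2 lists among the secondary safety variables "Incidence of late-onset sepsis in premature and low birth weight neonates", which is an incidence in a restricted group. SAP 8.12.4 carries the category over as "late-onset sepsis in premature and low birth weight neonates", one of the treatment-emergent adverse events (TEAEs) of special interest. These are reported as number and percentage of patients by treatment group.

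Three SAP provisions settle the denominator:

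- SAP 7: "The denominator for percentages will be based on the number of patients in the corresponding analysis set".
- SAP 8.12: "The analysis of the secondary safety endpoints will be performed using the safety analysis set".
- SAP 6.2: "The safety analysis set will consist of all randomized patients who received at least one dose of study medication".

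On who is enrolled, Protocol 7.1 says: "The study population will be hospitalized preterm and term neonates/infants who are expected to require PN for at least 28 days". Protocol 10.2 also admits infants with "volvulus, spontaneous intestinal perforation, or NEC" of Bell's stage 2B or higher.

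The table list in SAP 9 has Table 14.3.2.6a (special-interest events, safety set), Table 14.3.2.6b (the same by underlying disease group), and Tables 14.4.10.1 and 14.4.10.2 (by race and by ethnicity). None splits by gestational age or birth weight. Birth weight appears only in the listing of these events.

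**The concern.** The sepsis row restricts its numerator by name, while the stated rules leave its denominator unrestricted. Term infants of normal birth weight can never count as events in this row, yet they are counted as patients at risk. Two things follow. The printed incidence is lower than the incidence of the endpoint the protocol names. And because SAP 4.2 stratifies randomization by NEC status and site, not by gestation or birth weight, the arms may differ by chance in the share of infants who belong to the named group. That difference passes straight into the comparison of percentages. The SAP tests no hypotheses and reports no p-values, so the printed percentages are what a reader will use.

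**Working it through.** **Is there an implied exception?** Where the SAP wants another denominator it says so. In 8.12.5, laboratory shifts to the end of the extension use patients still in the study at the end of the initial phase. In 8.12.7, physical-examination shifts use patients evaluated at both time points. Section 8.12.4 says nothing comparable, so the general rule applies.

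**Size of the understatement.** The plan states no figure to reproduce. Let f be the share of the safety set that is premature or of low birth weight, and r the sepsis incidence in that group. With the numerator confined to the group as named:

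printed percentage = f × r

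Neither f nor r is in the documents. Assuming r = 20%:

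- f = 0.50: 0.50 × 0.20 = 10%
- f = 0.65: 0.65 × 0.20 = 13%
- f = 0.80: 0.80 × 0.20 = 16%

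With the named group as denominator, every case prints 20%.

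**Effect on the comparison.** If f is the same in both arms it cancels from the risk ratio, and only the absolute incidence is wrong. If it differs, the ratio of printed percentages with no true effect is f₁/f₂. To gauge the plausible range, take the 152 patients in the interim analysis (SAP 8.8) as 76 per arm (equal split assumed) and treat allocation as simple randomization:

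SD of the difference in f = √(2f(1 − f)/76)

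- f = 0.5: 1.96 SD = 0.159; ratio (0.5 + 0.0795)/(0.5 − 0.0795) = 1.38
- f = 0.7: 1.96 SD = 0.146; ratio (0.7 + 0.073)/(0.7 − 0.073) = 1.23
- f = 0.9: 1.96 SD = 0.095; ratio (0.9 + 0.0475)/(0.9 − 0.0475) = 1.11

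These are outer limits of ordinary chance, not expected values. A 65% v 50% split would print 13% v 10% with equal true risk, a ratio of 1.3.

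**NEC, for contrast.** Let g be the share with NEC at entry, r₀ the new-onset rate in the No NEC stratum, and w the rate of TEAE-qualifying NEC in the NEC stratum. The pooled percentage is (1 − g)r₀ + g·w. With r₀ = 5% and g = 0.3 (assumed):

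- w = 0: 0.7 × 5% = 3.5%
- w = 10%: 3.5% + 3.0% = 6.5%
- w = 30%: 3.5% + 9.0% = 12.5%

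Over g = 0.2 to 0.4 and w = 0 to 30% the pooled figure runs from 3% to 15%, so it can lie on either side of the at-risk rate. Table 14.3.2.6b, however, prints the No NEC stratum separately.

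**The case against.** The strongest reply is that little depends on this row. The safety analyses are descriptive. An equal share in both arms leaves the ratio untouched. A 65% v 50% split is about 1.9 SD with 76 per arm, so it is near the edge of chance. Even then the 3-point gap is smaller than the sampling SD of that difference, √[(0.13 × 0.87 + 0.10 × 0.90)/76] ≈ 5 points. Postmenstrual and chronological age are tabulated by arm at baseline, so a gross imbalance should show. Two bloodstream-infection endpoints cover infection without a maturity restriction. All of this stands and limits the weight of the point. None of it makes the printed incidence that of the named group.

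The table shells are a separate document and were not available. A footnote there could already set the denominator, in which case the SAP text needs only to say so.

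Three stronger readings are tempting, and the documents do not support them:

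- A reader might infer that the NEC percentage has the same fault. It mostly does not. Table 14.3.2.6b gives the No NEC stratum, unchanged pre-existing NEC is not a TEAE under 8.12.4, and NEC is a randomization stratum. What remains is that the pooled table and the race and ethnicity tables mix the strata, new onset is not separated from worsening, and the text of 8.12.4 mentions only treatment group for these events.
- A reader might infer that retinopathy of prematurity and the other listed morbidities also require preterm denominators. Neither document restricts those endpoints to a subgroup. An extra row for preterm infants would be optional.
- A reader might infer that every term infant is wrongly counted. A term infant of low birth weight can belong to the named group; those wrongly counted are term infants of normal birth weight.

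**Conclusion.** The point holds for the sepsis row. Under the SAP's stated rules its percentage is the incidence in the named group multiplied by that group's share of the safety set, and a chance imbalance in the share can appear as a treatment difference. The figures of 10% to 16% in place of 20%, and ratios of up to about 1.1 to 1.4 with no true effect, rest on assumed values of r and f, on 76 per arm, and on simple randomization. They also read the group as infants who are premature or of low birth weight; the plan does not say whether either feature is enough. For NEC only a clarification is needed. The consequence is limited to descriptive secondary safety results; the primary endpoint is unaffected.

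**What to change.** - **Sepsis.** In SAP 8.12.4 and in Tables 14.3.2.6a, 14.3.2.6b, 14.4.10.1 and 14.4.10.2, use as denominator for this row the safety-set infants born before 37 completed weeks or of low birth weight. The 37-week limit is the SAP's own definition of term, given in 8.11.1 for choosing growth charts. Neither document gives a low-birth-weight cut-off, so one must be stated before unblinding. Whole-set counts may stay alongside.
- **NEC.** Name the No NEC stratum of Table 14.3.2.6b as the main new-onset incidence result, show worsening or recurrence in the NEC stratum separately, and amend 8.12.4 so that its text matches the table list.

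No new data are needed. Gestational age at birth follows from postmenstrual and chronological age (SAP 8.3), birth weight is already used for eligibility and in the event listing, and the stratum is recorded at randomization. The cost is two definitions and a change to the table shells. The small downside is smaller denominators, and so less precise percentages, most noticeably in the race and ethnicity tables.
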